Number of Participants with Rationale	The data collected on crying time and standard deviations (SD) during the pilot phase (n=13, one diary was completed incorrectly) was consistent with observations made by Wolke et al. (2017). We estimated the average daily crying time over the two-week follow-up period to be 120 minutes with a SD of 46 minutes. To detect a minimum of 30 minutes additional reduction in crying time between the intervention and control groups, with 90% power and a two-sided 5% significance level, we would need 48 infants in each arm of the trial. If we allow for a 15% drop out rate, we will need to randomise 112 infants or 56 in each arm. Given there are three recruiting sites (UK, Australia, Switzerland), each site is to recruit 40 participants.
Study Intervention	Usual osteopathic care with osteopathic manual therapy treatment involving light touch for 10–20 minutes from one to four times over two weeks. Touch is directed at specific areas of the baby's body as deemed appropriate by the osteopath with the intent of bringing change to tissue function or fluid dynamics. Best practice advice will be drawn from the national UK guidance (NICE 2017, https://cks.nice.org.uk/colic-infantile)
Control Intervention	Usual osteopathic care including advice with non-specific generic light touch attention control on cranium, thorax, abdomen and sacral area in any order without any attempt by the osteopath to move or adjust soft tissues or modify fluid mechanisms. During touch, osteopaths undergo a cognitive task to divert attention from touch and avoid conscient

	interactions. Overall consultation duration is of 30-45 minutes, duration of targeted tension release is of 10-20 minutes, 1-4 times over two weeks.

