4.3 Study procedures

Pilot study

A pilot feasibility study was conducted in the UK to test the feasibility of a number of the trial's processes and procedures. These included: an estimation of recruitment rates, whether the osteopaths could be trained to deliver both the intervention and control arm of the trial as per protocol, parent/carer blinding and compliance, and accuracy rates for the electronic online data collection and crying diaries. Fourteen infants and parents were recruited, and 31 osteopaths were trained. Results from the pilot study showed that one in five parents with excessively crying infants who were approached for the study decided to participate in the trial. Only 25% of the osteopaths who underwent training in the trial protocol went on to recruit and treat infants into the trial. This prompted a change in recruitment strategy from general recruitment to the establishment of dedicated CUTIES trial clinics with only trial osteopaths and targeted advertising for these clinics. Compliance with electronic data capture was successful with parents preferring this system over paper-based collection. We asked parents about their group allocation at follow up and this showed that parental blinding was successful. We used the crying diaries to calculate the mean daily crying time and standard deviation between groups to determine sample size for the current protocol.

Randomisation procedure

Randomisation will be 1:1. Block randomisation will be used with a variable block size of 4 and 6 generated in real time online. Sequence generation is assured automatically by the web-based platform used for data management (CastorEDC – <https://uk.castoredc.com>). Allocation is provided by the same platform after the treating osteopath has confirmed consent, ensured the baby is healthy and a completed baseline questionnaire has been submitted.

Allocation is then registered within the system and is made available to the treating osteopath using the web-based platform.

Blinding

The chief investigator, the principle investigator, parents/carers, infants and statistician are blinded to allocation. Osteopathic practitioners (co-investigators), who provide care, and data manager, who will have no contact with participants, will not be blinded.

Parents/carers will NOT be informed which treatment arm their infant has been allocated to but they will be aware that the infant is receiving either the OMT or control intervention.

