There will be a standardised communication protocol between the osteopath and the parent/carer during both the OMT and control intervention sessions. It will be delivered at pre-set intervals during each session and include comments such as “your baby is doing very well”, “I have nearly finished checking and treating your baby”, “a few more minutes” and “we have now finished the treatment”. Each intervention session will last between 10 and 20 minutes. The osteopaths will be permitted to make soothing and/or playing noises with the infant during these sessions.

Should the parent wish to ask questions about the hands-on touch, the osteopath can talk in general terms about the explanatory theories associated with gentle light touch care but not about the touch they are giving, as the parent has consented to be blinded to this.

A parent/carer will be present throughout the treatment session and free to observe the delivery of intervention. However, parents/carers will remain 'blinded' throughout the active phase of the trial so that outcomes are not biased a priori by parent/carer expectations. Naming both intervention arms with equal suggestibility with respect to treatment supports this intention. To assess blinding, at the two-week follow-up, each parent/carer will be asked which group they believe their infant was allocated to, we will then compare these guesses between both groups using a Fischer's exact test.

Once the participant has completed and returned their follow-up questionnaire and their crying diary they can be informed about their infant's allocation. If they do not complete their follow-up information, their allocation can be divulged at 21 days or after, post randomisation. Unblinding of the parent will occur in the case of serious adverse events and or complaint and withdrawal from the trial.

To maintain blinding during statistical analyses, the statistician will also be blinded to group identity.

Data collection and management

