5 STATISTICS AND METHODOLOGY

5.1 Statistical analysis plan and sample size calculation

The analysis of the data will be carried out on the entire data collected by the international consortium. The Swiss data is therefore embedded in the overall analysis.

Sample size estimation

The data collected on crying time and standard deviations (SD) during the pilot phase (n=13, one diary was completed incorrectly) was consistent with observations made by (Wolke et al., 2017). We estimated the average daily crying time over the two-week follow-up period to be 120 minutes with a SD of 46 minutes. To detect a minimum of 30 minutes additional reduction in crying time between the intervention and control groups, with 90% power and a two-sided 5% significance

level, we would need 48 infants in each arm of the trial. If we allow for a 15% drop-out rate, we would need to randomise 112 infants or 56 in each arm. Each country is expected to enrol 40 participants or four patients from 10 secondary sites.

Descriptive statistics

Descriptive statistics will be used to summarise the characteristics of participants in each group in the trial. This will include baseline values, treatment schedules, compliance and follow-up. We will show number and percentage or mean and standard deviation for categorical and normally distributed continuous variables respectively. For data severely deviating from a normal distribution, we will present median and interquartile ranges. Probability of observed between groups difference will be calculated by using Fisher's exact, Chi2 test, Mann Whitney U test and, or Student's t-test as appropriate.

For crying time, the Bartlett's periodogram-based test for white noise will be used to test the assumption of constant mean and variance for each individual. Analysis of graphical representation will define which transformation would best model trend over time. If a clear change of effects happens abruptly over time, the data will be additionally analysed over separate time periods, by default separating the first week from the second. If such a trend exists, secondary analysis will also compare differences for indicators of this trend between groups.

Primary outcome analysis

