We will analyse the primary outcome of mean crying time using a multilevel mixed-effects generalised linear model (GLM) adjusting for lack of independence at site and at practitioner level. Mean crying time will be entered as the dependent variable and group allocation as the explanatory variable. The hierarchical multilevel datasets are assumed to have normally distributed random effects. Likelihood ratio test will be used to test for clustering effects. Results will be reported as between-group differences in average crying time in hours with 95% confidence intervals. P-values will provide the probability of this difference being null using Wald Chi2 test. If clustering effects cannot be identified ($p\text{-value} > 0.05$), further analysis (i.e. sensitivity analysis, adjusted analysis, etc.) will use simple logistic regression without accounting for lack of independence.

Secondary outcomes analysis

The same method will be used to test secondary outcomes. Categorical response variables using Likert scales (i.e. global change, parent satisfaction) will be analysed using a proportional odds model. Between group changes in parenting confidence score will compare changes from baseline by entering baseline score as an explanatory variable in the GLM model.

Proportion of participants who reported at least one adverse event will be compared between groups using a Fisher exact test. The same approach will be used to compare unexpected reactions (distress, crying, unsettled, vomiting, difficulties feeding, difficulties sleeping, other).

Exploratory analysis

We will:

- Explore explanatory variables at a practitioner level to model between osteopath heterogeneity if present.
- Describe eventual correlation between years of experience and treatment effects (*i.e.* analysis of trends and comparison for cut-off at 3 or less years versus more than 3).
- Investigate eventual association between post-graduate training and treatment outcomes (interaction term).
- Test whether adjunct treatments were similar between both groups to assess unequal treatment bias.

Sensitivity analyses

In a worse-case scenario in an intention to treat (ITT) analysis, we will replace those who are lost to follow-up and missing data for primary outcome with highest observed crying times values in the TTR group and lowest crying time values in the GTR group.

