5.2 Handling of missing data and drop-outs

Missing data from diaries will be accepted if at least eight separate entries over two weeks are provided. The average daily crying time will then be provided by averaging the crying time over the available days. As missing data cannot be assumed to be missing at random, complete case analysis is to be done. A sensitivity analysis will then evaluate effects on results with the worst-case scenario (imputation of highest observed effect if in control and lowest if in OMT group).

Drop-outs from treatment are to be followed-up and questionnaires delivered as if treatment had continued (ITT approach). Data from participants who have dropped-out or could not be followed will be replaced by new subjects.

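### The only missing-outcome sensitivity analysis fixed in the protocol is an extreme worst case, which at the planned loss cancels a true 30-minute effect and cannot separate a robust result from a fragile one

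*Protocol*

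**What the plan says.** Protocol section 5.2 counts a diary as usable if it has at least eight entries, and averages over the available days. It says the missing data cannot be taken to be missing at random, and then makes complete cases the main analysis. One sensitivity analysis for missing outcomes follows, and it is described twice:

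- Section 5.1, Sensitivity analyses: missing primary outcomes are replaced "with highest observed crying times values in the TTR group and lowest crying time values in the GTR group".
- Section 5.2: the worst case is described as "imputation of highest observed effect if in control and lowest if in OMT group".

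The other supporting analyses in section 5.1 (number of consultations, first versus second week, baseline imbalance, per protocol) do not deal with missing outcomes.

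The loss planned for is in section 5.1, Sample size estimation: "If we allow for a 15% drop-out rate, we would need to randomise 112 infants or 56 in each arm". On blinding, section 4.3 says "the statistician will also be blinded to group identity". The synopsis describes this as blinding to the group coding. Section 4.3 leaves the data manager unblinded.

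**The concern.** A sensitivity analysis should show whether the main conclusion survives plausible departures from its missing-data assumption. This one gives every missing TTR infant the worst value seen and every missing GTR infant the best. The size of the resulting shift depends mainly on how many infants are missing and how widely the outcome spreads, and hardly at all on why they are missing. If the shift at the planned loss is as large as the target difference, a real effect of the design size will nearly always disappear in the check, including when the missingness does no harm. The protocol doubts the assumption behind its own main analysis, so the check matters.

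Two smaller points go with it. The rule needs to know which arm is TTR, and the statistician does not. The two wordings also do not obviously point the same way.

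**Working it through.** **Inputs.** Target difference: "To detect a minimum of 30 minutes additional reduction in crying time between the intervention and control groups". Mean and SD: "We estimated the average daily crying time over the two-week follow-up period to be 120 minutes with a SD of 46 minutes". Allocation: "Randomisation will be 1:1". Power and size: "with 90% power and a two-sided 5% significance level, we would need 48 infants in each arm of the trial". Planned loss: 15%, 56 randomised per arm.

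**The plan's own figure.** n per arm = 2 × [46 × (1.960 + 1.282) / 30]² = 49.4, rounded up to 50. The stated 48 is close to this; power at 48 is 89.2% (normal approximation). For loss, 48 × 1.15 = 55.2, rounded up to 56. So 56 randomised with 48 analysable leaves 8 missing per arm (8/56 = 14.3%).

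**Assumptions added here.** Control mean 120 and TTR mean 90; equal loss in both arms; all the planned loss lacks a usable primary outcome; missing completely at random; extremes taken within each arm; clustering ignored. The protocol gives no outcome distribution, so several were tried. Benefit is GTR minus TTR, so positive favours TTR.

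**Closed form, normal model.** Among 48 observed infants, the highest TTR value averages about 192 min and the lowest GTR value about 18 min.

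- TTR mean after imputation: (48 × 90 + 8 × 192) / 56 = 104.6
- GTR mean after imputation: (48 × 120 + 8 × 18) / 56 = 105.4
- Benefit: 105.4 − 104.6 = about 0.9 min before rounding, instead of 30

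The shift is (8/56) × [(192 − 90) + (120 − 18)] = (8/56) × 204 = 29.1 min, or 204/56 = 3.6 min for each infant missing per arm.

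**Simulation (10,000 trials per setting, normal floored at zero, two-sided t-test at 5%, 56 per arm).**

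| True benefit | Missing per arm | Worst-case benefit | Significant for TTR |
|---|---|---|---|
| 30 | 8 | about 0.7 | about 3% (complete cases about 88%) |
| 30 | 5 | about 11 | about 20% |
| 30 | 4 | about 15 | about 32% |
| 30 | 3 | about 19 | about 49% |
| 45 | 8 | about 15 | about 31% |
| 60 | 8 | about 29 | about 81% |
| 0 | 8 | about −29 | 0% (significant for harm in about 80%) |

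**Other distributions, true benefit 30, 8 missing per arm.** The worst-case benefit is 0.9 (normal), −0.4 (gamma) and −1.5 (lognormal), with 3 to 5% significant. Arm means of 105 and 135 give 0.8 to −1.2. If highest and lowest are read across both arms together, the estimate reverses to between −6.5 and −10.4 min and essentially no trial is significant for TTR.

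**Direction of the wording.** Section 5.1 gives missing controls the lowest crying time. Section 5.2 gives them the highest *effect*. These agree only if effect means reduction in crying. Read as crying time, section 5.2 would favour TTR.

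**The case against.** A worst-case bound is legitimate, and the protocol labels it as a worst case. No passage makes the primary conclusion depend on it. A reader might infer that a real effect would have to be reported as not robust; the documents do not say so.

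A reader might also infer that the check gives the same answer whatever the data. It does not: a true 60-minute effect stays significant in about 81% of trials at the planned loss, and surviving such a bound is strong evidence. Nor is 15% a forecast. One of 14 pilot diaries was unusable (about 7%), and section 3.2 cites 91% sufficiently complete diaries in a population sample. At 4 to 5 missing per arm the effect is cut by half or more, but not removed.

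It is also tempting to say that a blinded statistician cannot run the analysis. That is wrong. Coded arms are available, so both directions can be run and labelled later, or the unblinded data manager can supply the direction. What stands is that the protocol does not say which.

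Finally, the SAP is not shown and may add milder analyses. The point therefore concerns the rule the protocol itself states, twice, as its check on missing outcomes. None of this changes the result near the design effect and planned loss.

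**Conclusion.** The point holds within limits. With a true benefit near 30 min/day and about 8 of 56 outcomes missing per arm, the stated analysis returns about zero under each distribution tried with within-arm extremes, and makes a true null look like about 29 min of harm, although the missingness was simulated as ignorable. In that setting it is uninformative about robustness. With 3 to 5 missing per arm it attenuates heavily (30 min to about 19 to 11 min), and it becomes informative for larger effects or smaller losses. The figures rest on SD 46, equal loss in both arms and no clustering.

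The unstated source of direction for the blinded statistician is a solvable operational gap. The two wordings need aligning. This is an inexpensive improvement to the plan; it does not undermine the primary analysis.

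**What to change.** Keep the rule of at least eight diary entries, so that the endpoint and the complete-case analysis are unchanged. For infants without a usable primary outcome, add a delta-adjusted (tipping-point) analysis:

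1. Multiply impute the infant's 14-day mean under missing at random from arm, baseline crying, age and any observed diary days.
2. Add a grid of deltas, for example 0, 15, 30, 45 and 60 min/day, to the imputed values in coded arm A only, coded arm B only, and both.
3. Report the delta at which the conclusion changes.

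Because this treats the coded arms symmetrically, it needs no unblinding. Keep the extreme imputation only as a labelled bound, run in both directions in coded arms, and state whether the extremes are taken within or across arms. Reword section 5.2 in terms of crying time so that it matches section 5.1.

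The cost is some extra programming and a grid of results in place of one number. No additional data are needed.

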5.2 Handling of missing data and drop-outs

Missing data from diaries will be accepted if at least eight separate entries over two weeks are provided. The average daily crying time will then be provided by averaging the crying time over the available days. As missing data cannot be assumed to be missing at random, complete case analysis is to be done. A sensitivity analysis will then evaluate effects on results with the worst-case scenario (imputation of highest observed effect if in control and lowest if in OMT group).

Drop-outs from treatment are to be followed-up and questionnaires delivered as if treatment had continued (ITT approach). Data from participants who have dropped-out or could not be followed will be replaced by new subjects.

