It is recognised that parents/carers are often in crisis when they seek support and care for their 'colicky' infants and that they expect the outcome of that care to have an almost immediate effect. This study has therefore been designed to look at only the short-term impact of care. The reasons for this are two-fold: i) to limit the stress on the parent/carer (the peak time for crying is during the infants first six to eight weeks of age), and ii) because normally the symptoms of excessive crying, unsettledness and distress are self-limiting and start resolving around nine to 12 weeks of age (Wolke et al., 2017). Parents/carers in both groups will receive recommended advice and information drawn from national clinical guidelines (NICE 2017). The inclusion of a 'non-touch' control group was not possible due to the inability to blind the parents/carers of infants in such a group.

The aim of this study is therefore to evaluate the effectiveness of osteopathic manual therapy care for excessively crying, unsettled and distressed infants under 10 weeks old. The study will compare the effect of osteopathic specific light touch manual therapy care delivered with therapeutic intent with a non-specific light touch manual intervention. The trial will provide data regarding the belief of both osteopaths and parents/carers, that the 'therapeutic intent' associated with the directed osteopathic light touch is the active element in delivering benefits.

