Attrition bias could occur if the number of consultations is unevenly distributed between groups. Therefore, secondary analysis will verify that results are not influenced by uneven distribution of number of consultations. This will be done using random-effects generalised least-square regression adjusting for lack of independence at practitioner level.

Complementary confirmatory analysis

- Separate analysis between 1st and 2nd week (stratified analysis underpowered).
- If baseline imbalance (p -value <0.10) is observed, a secondary analysis with adjustment for these variables will be run to confirm results.
- Per protocol analyses.

All analysis will be intention-to-treat (ITT) except for a secondary per protocol analysis on the primary outcome. All P values will be two sided, and the significance level set at 5%. All statistical analysis are to be done using StataCorp. 2017. Stata Statistical Software: Release 15. College Station, TX: StataCorp LLC. Statistical analysis is managed by [name] who is responsible of preprogramming the entire analysis prior to data collection, of justifying protocol deviation and obtaining approbation from the trial steering committee whilst still blinded from allocation, of running the analysis and delivering the statistical report.

Stopping rule

There are no statistical stopping rule. The trial will be stopped if another high-quality definitive research trial shows that this type of intervention is either highly effective, or is harmful and renders the continuation of this trial inappropriate. The Data Monitoring Committee (DMC) will review the data after 75 infants have been recruited and followed up, to determine progress. The trial will not proceed if more than half the parent participants do not complete their crying diaries, withdraw from the study or if the DMC considers that participants experience too many serious adverse events.

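### Doubt about missing at random is used to justify complete-case analysis; the reasoning is reversed and leaves the primary contrast open to bias

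*Protocol*

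**What the plan says.** Protocol section 5.2 sets a threshold for a usable diary: "Missing data from diaries will be accepted if at least eight separate entries over two weeks are provided". For a diary that passes: "The average daily crying time will then be provided by averaging the crying time over the available days". It then gives the principle for the rest: "As missing data cannot be assumed to be missing at random, complete case analysis is to be done". A worst-case imputation follows as a sensitivity analysis. Section 5.1 (Sensitivity analyses) describes it as giving the highest observed crying to missing infants in the osteopathic (TTR) arm and the lowest to those in the control (GTR) arm.

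The primary model in section 5.1 takes one mean per infant as the dependent variable and allocation as the explanatory variable, with site and practitioner levels. The same section says: "All analysis will be intention-to-treat (ITT) except for a secondary per protocol analysis on the primary outcome". Section 8.3 adds that data gathered before a withdrawal will be used.

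On the course of crying, section 2 says that "normally the symptoms of excessive crying, unsettledness and distress are self-limiting and start resolving around nine to 12 weeks of age". Section 7.2 expects strong regression to the mean.

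**The concern.** A trialist who doubts that data are missing at random (MAR) has a reason to avoid complete-case analysis, not to choose it. A likelihood model on the daily entries is valid if stopping depends on crying already recorded. Complete-case analysis with allocation as the only covariate is not valid even then. It needs stopping to be unrelated to crying within each arm. Section 5.2 weakens the assumption and then picks the method that needs the stronger one.

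Two things follow. First, who is excluded may depend on crying. If treatment works and parents of infants who cry most give up the diary, the control arm loses more of its worst infants and the difference shrinks. If parents stop once the infant has settled, the osteopathic arm loses more of its best infants and the difference again shrinks. Second, a diary kept only for days 1 to 8 is treated as equal to a full one, although the protocol expects crying to change over the fortnight.

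The effect sought is modest relative to the spread, so a loss of a few minutes matters.

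**Working it through.** **Inputs from the protocol (section 5.1).** Mean and spread: "We estimated the average daily crying time over the two-week follow-up period to be 120 minutes with a SD of 46 minutes". Target difference 30 min/day, power 0.90, two-sided alpha 0.05. Stated need: 48 per arm.

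**The plan's own figure.** n per arm = 2 × (1.960 + 1.282)² × 46² / 30² = 49.4, so 50. With 48 per arm, SE = 46 × √(2/48) = 9.39 and power = Φ(30/9.39 − 1.96) = 0.89. The stated 48 is close enough to use.

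**Step 1: error for one infant.** Days 1–8 centre on day 4.5 and days 1–14 on day 7.5. Under a linear fall, the infant's mean is overstated by 3 × the daily slope. The slopes are assumptions:
- 135 to 105 min: 3 × 30/13 = 6.9
- 150 to 90 min: 3 × 60/13 = 13.8
- 180 to 60 min: 3 × 120/13 = 27.7

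**Step 2: what reaches the contrast.** This error cancels if both arms stop equally and trends are parallel. Otherwise the bias is the difference in the proportion stopping early × 3 × slope. For slopes of 2 to 10 min/day (shift 6 to 30 min), a 10-point difference gives 0.6 to 3.0 min and a 20-point difference 1.2 to 6.0 min.

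**Step 3: simulation of the whole rule.** 100,000 infants per arm, SD of the 14-day mean 46, true reduction 30. Assumed: daily residual SD 40, and a fall of 4 or 8 min/day (the two figures in each cell). The daily model includes allocation-by-day terms.

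| Stopping | Effect over time | Section 5.2 rule | Daily mixed model |
|---|---|---|---|
| Random, 30% in each arm | constant | 29.9, 30.4 | 29.8, 30.2 |
| Random, 30% in each arm | growing | 29.0, 28.6 | 30.2, 29.8 |
| Random, 10% control, 30% osteopathic | constant | 29.0, 28.7 | 29.9, 30.2 |
| Random, 30% control, 10% osteopathic | constant | 30.5, 31.8 | 29.7, 30.2 |
| After a recorded high-crying day | constant | 25.9, 25.3 | 29.7, 30.2 |
| After a recorded settled day | constant | 24.7, 24.8 | 29.8, 30.2 |
| On an unrecorded high-crying day | constant | 25.4, 24.9 | 27.6, 27.2 |
| On an unrecorded settled day | constant | 23.7, 23.7 | 27.6, 28.3 |

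A second set-up used infant SD 42 and daily SD 70, which reproduce the plan's SD: √(42² + 70²/14) = 46. With 60 per arm and stopping driven by the last three recorded days, the section 5.2 rule gave 27.0, or 24.0 with a stronger link. The daily model gave 29.9 and 29.8, with its variances treated as known. At the weaker link, 22% of control and 13% of osteopathic infants fell below eight days. With lower loss (12% and 7%), the bias was about 1.7 min.

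**Step 4: is the interaction needed?** In the second set-up, let the effect grow from 0 to 60 min (14-day mean 30). The section 5.2 rule gave 28.5 and 27.3 for the weaker and stronger link. A daily model without allocation-by-day terms gave 24.8 and 22.4, which is worse. With those terms it returned to about 30.

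**Step 5: consequence for power.** With 48 per arm and SD 46, losing 2 min gives Φ(28/9.39 − 1.96) = 0.85. Losing 7 min gives Φ(23/9.39 − 1.96) = 0.69.

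**The case against.** The plan does not leave the excluded infants out everywhere. Its worst-case analysis returns them under intention-to-treat and needs no MAR assumption. Section 5.1 also plans a check of trend and separate analyses of weeks 1 and 2. This should be acknowledged, and a reader should not infer that missing data are untested. But the worst case can move the estimate only against osteopathic treatment. If the primary bias already runs towards no effect, it cannot reveal it. It bounds the result without repairing the primary estimate.

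Attrition may be low. Section 3.2 cites 91% of diaries sufficient for analysis in the validation sample, and 13 of 14 pilot diaries were usable (sections 4.3 and 5.1). That stands, and it is why the lower end of the range is near 2 minutes.

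The mixed model is favoured when stopping depends only on recorded days, which is MAR by construction. Section 5.2 doubts exactly that. This also stands: when stopping depended on the unrecorded day, the mixed model was still about 2 to 3 minutes short with a constant effect. It was nevertheless closer to the truth than the section 5.2 rule.

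A steady fall in every infant is not what the protocol says. Section 2 puts the peak at six to eight weeks and section 4.1 admits infants from 8 days, so some may rise first. The slopes in step 1 are illustrations.

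**Conclusion.** The point holds as a fault of reasoning in a fixed primary rule, with a conflict between that rule and the intention-to-treat statement. The contrast is open to bias. Under outcome-related stopping and a constant effect, the bias is roughly 2 to 7 min/day of the 30-minute target, towards no effect. It is nearer 2 min at low attrition, and about zero when stopping is random and equal and the effect is constant. The stopping models, slopes and daily SDs are assumptions, since the protocol gives none of them.

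Two stronger readings are tempting and are not supported. One is that the result is biased as a matter of fact: nothing in the protocol shows how stopping will relate to crying or to arm, and random stopping that is commoner in the control arm can even enlarge the difference slightly. The other is that the 7 to 28 minutes in step 1 is error in the treatment effect. That figure is one infant's error. Most of the simulated bias comes from outcome-related stopping. Averaging the available days adds little to the contrast unless early stopping differs by arm or the effect changes over time.

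**What to change.** Delete the sentence in section 5.2 that derives complete-case analysis from doubt about MAR. Make the primary analysis a linear mixed model on the daily diary minutes of every infant with at least one diary day. Use fixed effects for allocation, categorical diary day and their interaction, an infant random effect, and the planned site and practitioner levels. Report the allocation contrast averaged equally over days 1 to 14, which keeps the present estimand. The interaction is essential: without it the estimate leans to the early days and can be worse than the current rule if the effect grows.

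Keep the 8-of-14 available-day mean and the worst-case imputation as sensitivity analyses. Add a graded delta analysis in which unrecorded days are shifted by increasing amounts, separately by arm, because the mixed model relies on MAR given the recorded days. Infants with no diary entry add nothing to the mixed model, so these sensitivity analyses must cover them.

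The cost is revised wording and a slightly longer model. The daily minutes are already collected. The drawback is the MAR assumption, which should be stated openly. Whether to adjust for baseline crying and age, and whether to keep total crying time as an outcome, are separate questions.
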